Secondary outcomes	 For patients who benefited from gabapentin, identification of the lowest dose that was effective in reducing pain scores, as shown by a 50% reduction in the NCCPC-R score compared to baseline during days 11-19 on active drug For patients who benefited from gabapentin, identification of the maximal effect dosage as measured by the largest improvement in the NCPCC-R score compared to baseline during days 11-19 on active drug. Identification of the latency time in days to the onset of maximum relief of pain and irritability as measured by the NCCPC-R score over days 0-19. Adverse Events Collection demonstrates the AE on treatment arm do not exceed the frequency found in 	
	gabapentin. PROMIS-57 scores on the treatment arm compared to the	
Exploratory outcomes	placebo arm.	
Outcome measures	Primary: NCPCC-R Secondary: NCPCC-R, Adverse Events Collection Exploratory: PROMIS-57	

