3.4. Outcomes

1. Primary Outcome: The mean pain and irritability score on the NCCPC-R through days 11-19 on active drug compared to placebo.

[figure not shown]
An 11-point decrement in the NCCPC-R score with no rebound x 3 days is considered clinically meaningful minimum change (improvement).

Secondary Outcomes:

- 2. For patients who benefited from gabapentin, identification of the lowest dose that was effective in reducing pain scores, as shown by a improvement the NCCPC-R score compared to baseline during day 11-19 on active drug.
- 3. For patients who benefited from gabapentin, identification of the maximal effect dosage as measured by the largest improvement in the NCPCC-R score compared to baseline during days 11-19 on active drug.
- 4. Identification of the latency time in days to the onset of maximum relief of pain and irritability as measured by the NCCPC-R score over days 0-19.
- 5. Adverse Events Collection demonstrates the AE on treatment arm do not exceed the frequency found in the Product Monograph for children receiving gabapentin.
- 6. Exploratory Outcome: PROMIS-57 scores reported by parent/caregiver are improved on the treatment arm compared to the placebo arm.

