If a subject who otherwise meets inclusion criteria has not undergone the evaluation for treatable, nociceptive-inflammatory causes of pain and irritability described by the PIUO Pathway, then we will conduct a PIUO Pathway evaluation first. If a treatable cause is identified, then the child will be referred back to their primary health care provider, and will not be enrolled in the gabapentin trial. If no treatable cause is found, then the child may continue onto the gabapentin trial. It is expected that undertaking a full PIUO Pathway evaluation may take 2-4 weeks time.

Baseline Visit

The Baseline Visit will be in person and will last approximately 2 hours. The following activities will be conducted prior to drug dispensing:

- Medical history: The participant will be asked to confirm findings in the Health Information Form. The following clinical information will also be collected for each participant:
 - o Any pre-existing medical conditions/signs/symptoms as part of the medical history.
 - o List of concomitant medications, dosage and date of treatment initiation
- Vital signs: Seated blood pressure (BP), heart rate (HR), respiration rate, oxygen saturation (SpO2), temperature, weight and height will be recorded.
- A head to toe physical exam will be performed
- The participant will be asked to complete the following at the Baseline Visit:
 - o Demographic Information (Appendix 3)
 - o Pain Survey (Appendix 5)
 - o NCPCC-R (Appendix 7)
 - o PROMIS-57 (Appendix 8)

In addition to reviewing all previous clinical work-up related to pain and irritability, we will establish a baseline for participants' expectations to the effectiveness of gabapentin. Pain is highly modifiable by psychological factors such as beliefs and expectations, which may influence treatment response (via placebo analgesia). This is especially important in this context of children with SNI where caregivers play a key role in assessment and management of pain and a placebo-by-proxy effect might occur based on the parents' perceptions/behavior. To evaluate the Impact of Expectations all families will be asked at the Baseline Visit if they expect participation in the trial will be of benefit to their child and at Follow Up they will be asked if the trial was of benefit to them and/or their child. They will also be asked after each sequence whether they believe their child received medication or placebo.

Randomization

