3.10. Statistical Methods

All data will be entered into a REDCap database, either directly from participants using a web-based entry system, or for those using paper, transferred from data collection sheets by a research assistant. The study cohort will be described in tables with descriptive statistics (mean, median and standard deviation) where appropriate. The primary method of analyzing the data was by systematic visual graphing of the pain scale over the exposure/placebo conditions. This is the method recommended by the CONSORT collaboration, extension for N-of-1 studies (CENT).⁵⁸

Data analysis for the primary outcome will be conducted within each N-of-1 trial and will also be aggregated across trials using measurements taken on days 11-19.

For each individual, the pain and irritability score on the NCCPC-R will be calculated over days 11-19 for both the treatment and control periods. These means will then be compared statistically using a Bayesian model, reporting the posterior mean difference using a non-informative prior for the means and variance. The posterior probability that the mean of the treatment is greater than the mean of the control will also be reported. Because of the use of non-informative priors, this analysis is very similar to a t-test.

We will also aggregate the means across participants using Bayesian linear mixed models in order to compare the average effect of the treatment as well as obtain better estimates of each individual's effect through borrowing of strength from others' data.

Additional analyses

Secondary outcomes will be assessed as follows:

- For each patient who benefits from gabapentin, the lowest dose that was effective in reducing pain scores will be calculated as the lowest dose that gives at least an 11 point reduction with no rebound over 3 days in the NCCPC-R score compared to baseline during day 11-19 on active drug. The set of lowest doses will be summarized descriptively.
- For each patient who benefits from gabapentin, the maximal effect dose will be calculated as the dose that gives the largest improvement in the NCPCC-R score compared to baseline during days 11-19 on active drug. The set of lowest doses will be summarized descriptively.

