^{*}If the child participated in the PIUO Study within the last 6 months these items will already be completed and only a Health Update is necessary to complete prior to drug dispensing. If the child did not participate in the PIUO Study all items will be completed and the PIUO Pathway will be implemented prior to drug dispensing. If a treatable cause for the child's PIUO is uncovered, the child will be withdrawn from the gabapentin trial.

Version 3.0 October 4, 2020 Page 39 of 45

 Table 4: Medication and Placebo Assessment Schedule for all subjects

Day	Health Update	Concomitant Medications	NCCPC-R	Pain Survey	PROMIS-57
1	X	X	X	X	X
2					
3					
4					
5			X	X	
6					
7					
8			X		
9					
10					
11	X		X		
12			X	X	X
13			X		
14			X		
15			X		
16			X	X	X
17			X		
18			X		

Version 3.0 October 4, 2020 Page 40 of 45

19			X	X	X
20					
21					
22			X		
23					
24					
25					
Switch Over*	X	X	X	X	X

^{*}Day 1 or 26 if switching over, not both

Version 3.0 October 4, 2020 Page 41 of 45

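### The rules that label a gabapentin dose as effective use change from baseline on active drug only, so falls that also occur on placebo count as dose effects in secondary outcomes 2 and 3

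*Protocol*

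**What the plan says.** Section 3.4 (Outcomes) gives the threshold directly under the primary outcome: "An 11-point decrement in the NCCPC-R score with no rebound x 3 days is considered clinically meaningful minimum change (improvement"). It does not say there what the decrement is measured from.

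Section 3.10 (Additional analyses) supplies the reference. The lowest effective dose is the lowest one giving "at least an 11 point reduction with no rebound over 3 days in the NCCPC-R score compared to baseline during day 11-19 on active drug". For the second dose outcome, "the maximal effect dose will be calculated as the dose that gives the largest improvement in the NCPCC-R score compared to baseline", over the same days on active drug. Neither sentence contains a placebo term.

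Both outcomes are restricted to a subset; section 3.4 begins the first with "For patients who benefited from gabapentin, identification of the lowest dose that was effective in reducing pain scores". The protocol does not define who belongs to that subset. The Trial Summary (section 1) gives a different criterion for the lowest effective dose: "as shown by a 50% reduction in the NCCPC-R score compared to baseline during days 11-19 on active drug". That too is measured from baseline in the active period alone.

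Baseline is not defined. Section 3.8 has the NCCPC-R completed immediately before the Baseline Visit and also lists it at that visit. Table 4 in section 6.2, "Table 4: Medication and Placebo Assessment Schedule for all subjects", has one score on Day 1, then days 5, 8, 11 to 19 and 22. No averaging over several pre-dose days is mentioned.

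Section 3.8 also warns that "a placebo-by-proxy effect might occur" through the caregivers who do the scoring.

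**The concern.** The design has each child serve as their own control, so that change on gabapentin can be set against change on placebo. The two dose outcomes do not use that control. A child whose score falls 11 points for three days in both periods meets the effective-dose rule just as a child who improves only on gabapentin does. The protocol expects caregiver-mediated placebo response and already collects the scores that would reveal it, yet the rule leaves them out.

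At stake are the descriptive summaries of lowest effective dose and maximal-effect dose. Section 2.1 says the results should help in designing a larger trial. If some of the doses come from children whose fall was not due to the drug, the summaries cannot be read as dose-response information.

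**Working it through.** There is no stated figure to reproduce: section 3.6 says that within-patient variability and expected effect were unknown and that power was not calculated. The SD, the correlation and the placebo response below are therefore assumptions.

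**Chance of meeting the rule with no drug effect**

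Model: one baseline score B with mean m + s and standard deviation SD, where s is the fall not due to drug; nine scores on days 11 to 19 with mean m and the same SD; normal and independent. Success means any three consecutive days all at or below B − 11. Given B, each day succeeds with probability Φ((B − 11 − m)/SD). Averaging over B by simulation (at least 100,000 children per setting) gives:

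| Assumed SD | s = 0 | s = 5 |
|---|---|---|
| 6 | 5% | 18% |
| 8 | 10% | 24% |
| 10 | 16% | 29% |
| 15 | 25% | 35% |

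Sensitivity:
- With lag-1 correlation 0.5, SD 8 gives 16% (s = 0) and 32% (s = 5).
- If the three days must be the blocks 11–13, 14–16 or 17–19, SD 8 with s = 5 gives 19% instead of 24%.

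Among 10 children at SD 8, the chance that at least one meets the rule without any drug effect is 1 − (1 − 0.104)^10 = 67% with s = 0, and 1 − (1 − 0.24)^10 = 94% with s = 5.

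**What each possible repair would do (SD 8, independent days)**

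*Same rule in both periods.* With s = 5 and no drug effect, 24% are expected to meet it on each treatment, so the two counts agree on average and the comparison is fair at group level. As a label for one child it stays noisy: meeting the rule on gabapentin but not on placebo has probability 0.24 × (1 − 0.24) = 18%.

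*Difference of 9-day means of at least 11.* The standard error is 8 × √(2/9) = 3.77, and the false rate is Φ(−11/3.77) = 0.2%, whatever s is. Doses still change over days 11 to 19, however. A 20-point effect confined to days 17–19 shifts the 9-day mean by only 20/3 = 6.7 points, so it is detected with probability Φ(−(11 − 6.7)/3.77), about 13%. The written rule detects it 60% of the time (simulated, s = 0). An effect on three of the nine days would have to be 33 points to shift the mean by 11.

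*Difference of 3-day means on matched days of at least 11.* The standard error is 8 × √(2/3) = 6.53. The same late 20-point effect is found at its own step with probability Φ((20 − 11)/6.53) = 92%. The false rate is Φ(−11/6.53) = 4.6% per step, or 1 − (1 − 0.046)³ = 13% over three steps. It does not rise with s.

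**The case against.** The strongest objection is that the protocol never says the 11-point rule decides who benefited. Section 3.10 takes the benefiting children as given and then uses the rule to pick a dose within that group. Membership could rest on the per-child gabapentin-versus-placebo comparison in the same section, or be left to an analysis plan that is not shown. This stands: a reader might infer a placebo-blind responder definition, but the text supports only an undefined term. It does not rescue the dose rules, which section 3.10 does fix, and fixes without placebo.

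Three other readings go too far:

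- **That the trial's main result or individual answers are compromised.** They are not. The primary outcome, the per-child posterior difference and the pooled model all compare gabapentin with placebo, and section 3.8 has families shown both arms. No responder rate is an outcome.
- **That regression to the mean is built in.** It is plausible but not shown. Entry is on the Pain Survey (section 3.2), not on a high Day 1 NCCPC-R.
- **That baseline is certainly one score.** The schedule suggests this; the protocol does not state it.

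It is also fair to object that the percentages depend on assumed inputs, and that a 9-day mean-difference criterion would lose children who respond only at later dose steps. Both points stand. The first is why a range is shown; the second is why the fix below does not use a 9-day mean.

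**Conclusion.** The concern holds for secondary outcomes 2 and 3. As written, both dose rules credit to gabapentin any sufficient fall from baseline during the active period, including falls that placebo would also produce. The competing 50% criterion in the Trial Summary has the same gap.

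The size cannot be derived from the protocol. The rates of about 5% to 25% without placebo response, and about 18% to 35% with a 5-point one, rest on normal scores, independent days, one baseline score, SD 6 to 15 and a lenient reading of the three-day condition. They apply to the 11-point rule; the maximal-effect rule has no threshold and always names a dose for every child in the subset. The correction is worth making before analysis, but it leaves the primary conclusions untouched.

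**What to change.** In sections 3.4 and 3.10, with section 1 brought into line:

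1. Apply the 11-point, three-day rule identically to days 11 to 19 of the placebo period, and report both counts side by side.
2. Define benefiting from gabapentin once, by a within-child gabapentin-versus-placebo comparison on matched study days, for example by dose step. Steps should follow the child's own dosing table: the two weight groups change dose on different days, and for children of 15 kg or more the scheduled reduction begins on day 18. Report the comparison with its uncertainty, since a 3-day contrast is noisier than a 9-day one.
3. State which NCCPC-R score, or average of scores, is baseline in each period.
4. Reconcile the 11-point and 50% criteria.

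This changes analysis wording only. It needs no new data, because the placebo days are already scored, and it leaves dosing alone. The cost is that fewer children may count as benefiting, so the descriptive dose summaries would rest on a smaller subset of the 10.

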2.2. Objectives

The primary objective of the trial is to evaluate the effectiveness of gabapentin to decrease pain and irritability in children with SNI, when the source of pain and irritability is attributed to neurological dysregulation (nociplastic pain), as measured by parent reported pain scores. This objective corresponds to the primary outcome listed in section 3.4.1.

We will compare the gabapentin versus placebo along an escalating dose range for both individual subjects and for the group. We will aggregate the results of the completed N-of-1 trials across all subjects to estimate the group level comparative effectiveness of gabapentin in reducing pain and irritability.

The secondary objectives are to:

- 1. Identify the optimal dosing of gabapentin in reducing pain and irritability (Corresponds to secondary outcomes 3.4.2 and 3.4.3).
- 2. Identify the latency time for gabapentin to show effectiveness (Corresponds to secondary outcome 3.4.4).
- 3. Evaluate the safety and tolerability of gabapentin (Corresponds to secondary outcome 3.4.5).
- 4. An Exploratory objective will be to evaluate whether parent/caregiver stress and function improve if gabapentin reduces children's pain and irritability. This objective corresponds to the Exploratory outcome listed in section 3.4.6.

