3.6. Sample size

We will enroll 10 participants in the gabapentin trial. In personalized trials, sample size refers to the number of assessments for each patient. As we had no prior data from which to estimate within patient day-to-day variability in pain scores nor an expected effect size for symptom reduction when comparing gabapentin to placebo in this population, we did not calculate statistical power a priori for the number of assessments per treatment period. Rather, the sample size for each personalized trial was based on collecting the maximal amount of data expected to be tolerable from the perspective of patient study burden. Ten participants is a sampling number based on current recruitment into the PIUO Study (REB #H16-03288) from which we expect to draw the majority of participants for this trial. This number, with the repeated measures obtained throughout the treatment periods should provide sufficient data to address the study goals.

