Missed visits

If a participant misses a scheduled study visit or contact with prior permission, the researchers will try to contact him/her and schedule a visit as soon as possible. Participants who stop taking the study medication for any reason will be asked to complete the Final Study Visit.

Withdrawal from trial

A participant may be withdrawn from the trial due to the following reasons including, but not limited to:

- Participant's request
- Severe Adverse Events (SAE) and/or other safety reasons
- A new health condition appears that is suspected to require care or medications prohibited by the protocol

• It is in the participant's best interest according to the Investigator's clinical judgment

Participants are free to withdraw from the study at any time and for whatever reason, specified or unspecified, and without prejudice to his or her medical care by a physician.

All premature discontinuations and their causes must be documented by the Investigator on the appropriate CRF pages. The reason for, and date of, the discontinuation, and the date of the last dose of the study medication, must be recorded in the appropriate section of the CRF. While the treatment with the investigational product will discontinue if a participant withdraws from the trial, participants not completing the entire study should be fully evaluated (i.e., last study contact and follow up procedures performed), wherever possible.

Withdrawn participants will be replaced via ongoing recruitment in order to meet the goal of obtaining data from 10 participants completing the trial.

Early termination visit

If a participant withdraws or is removed from the trial for any reason prior to the completion of the trial, the reason for, and date of, the discontinuation, and date of the last dose of study drug, must be recorded in the appropriate section of the Case Report Form (CRF).

At the time of discontinuation, every effort should be made to ensure that: (1) Procedures and evaluations scheduled for the End of Study are performed, including the assessment of AEs. (2) Study drugs are returned and inventoried. (3) Study staff make an appointment for a safety follow-up visit if required.

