- The latency time in days to the onset of maximum relief of pain and irritability as measured by the NCCPC-R score will be the day that gives the largest improvement in the NCPCC-R score compared to baseline during days 0-19 on active drug. The set of latency times will be summarized descriptively.
- Adverse Events will be compared between treatment arms descriptively.
- PROMIS-57 scores reported by parent/caregiver will be computed for each patient on each arm by averaging the scores taken on days 12, 16 and 19 and comparing these mean scores. The differences in mean scores between the treatment and placebo arms will be summarized descriptively.

Analysis population and missing data

For the primary outcome, any missing days will be excluded from calculation of the mean.

For secondary outcomes, missing values will be disregarded in the sense that only observed values will be used to compute the lowest dose, maximal effect dose, latency time and PROMIS-57 mean scores.

Analyses will use the intent-to-treat principle meaning that observations in a period will be ascribed to the treatment to which that period was randomized.

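### Secondary outcome 5 sets out to demonstrate that adverse events do not exceed the Product Monograph, which the planned placebo comparison does not address and about 10 exposed children cannot show for most event types

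*Protocol*

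**What the plan says.** Secondary outcome 5 in Protocol section 3.4 reads: "Adverse Events Collection demonstrates the AE on treatment arm do not exceed the frequency found in the Product Monograph for children receiving gabapentin". The Trial Summary (section 1) carries the same outcome, partly cut in the text available.

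The objective linked to it in section 2.2 is milder: "Evaluate the safety and tolerability of gabapentin (Corresponds to secondary outcome 3.4.5".

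The only adverse event analysis given in section 3.10 is: "Adverse Events will be compared between treatment arms descriptively". It names no monograph rate, margin or comparison with an external source.

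On size, section 3.6 says "We will enroll 10 participants in the gabapentin trial" and explains that "Ten participants is a sampling number based on current recruitment into the PIUO Study". It adds that "we did not calculate statistical power a priori for the number of assessments per treatment period", yet concludes: "This number, with the repeated measures obtained throughout the treatment periods should provide sufficient data to address the study goals". Section 3.8 provides that "Withdrawn participants will be replaced via ongoing recruitment in order to meet the goal of obtaining data from 10 participants completing the trial", and section 3.12 says safety analyses use all data. Slightly more than 10 children may therefore contribute safety data.

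Section 3.3 lists known side effects without frequencies.

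**The concern.** An outcome should name what is measured. This one names a finding: no excess over a published rate. Two problems follow.

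- **Mismatch.** The objective asks for an evaluation, the outcome asks for a demonstration against the monograph, and the analysis compares the two study periods. Completing the planned analysis in full would leave the outcome unanswered.
- **Size.** Repeated pain scores add information about pain, but they do not add children exposed to gabapentin. For adverse event frequency the denominator stays at about 10.

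What is at stake is the safety statement in the report. Section 2.1 presents this as the first randomised placebo-controlled study in this population and indication, intended to inform a larger trial, including on adverse effects. A statement that events did not exceed the monograph would be read as reassurance that the data cannot give. The comparison that the design does support, each child against his or her own placebo period, is not the stated safety outcome.

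**Working it through.** **Stated figure.** The sample size of 10 comes from expected recruitment. No significance level, power, margin or reference rate is given, so there is no calculation to reproduce.

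**Inputs.** n = 10 exposed children (section 3.6). The reference rate r for any event is not in the protocol, so every value of r below is an assumption.

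**1. What zero events can show.** The exact upper limit for 0/n is 1 − α^(1/n).
- One-sided 95%: 1 − 0.05^(1/10) = 0.259.
- Two-sided 95%: 1 − 0.025^(1/10) = 0.308.

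No value of r is used here. If r is below about 26% (or 31%), non-excess cannot be shown even when no child has the event. One event in 10 raises the limits to 39.4% and 44.5%.

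Replacing withdrawals changes little. The one-sided limit is 1 − 0.05^(1/12) = 22.1% for 0/12 and 1 − 0.05^(1/14) = 19.3% for 0/14.

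**2. Children needed to demonstrate non-excess.** With zero events, n = ln(0.05)/ln(1 − r), rounded up. An exact one-sided 5% test with 80% power, when the true rate is half of r, needs many more:

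| Assumed r | n if no events occur | N for 80% power, true rate r/2 |
|---|---|---|
| 5% | 59 | 361 |
| 10% | 29 | 179 |
| 15% | 19 | 118 |
| 20% | 14 | 82 |

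**3. Simply checking whether the observed proportion is at or below r (illustration only).** With X ~ Bin(10, r), the chance that the observed proportion exceeds r when the true rate equals r is P(X > 10r). The last column gives the chance that the check still passes when the true rate is 2r.

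| Assumed r | Exceeds by chance, true rate r | Passes, true rate 2r |
|---|---|---|
| 3% | 26% | 54% |
| 5% | 40% | 35% |
| 8% | 57% | 18% |
| 10% | 26% | 38% |
| 15% | 46% | 15% |
| 20% | 32% | 17% |

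The pattern is uneven because counts out of 10 move in steps of 10%. The range of 26% to 57% belongs to the rates examined and is not a bound. Just below r = 10%, for example, the chance approaches 1 − 0.9^10 = 65%.

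A formal test for excess fares no better. An exact one-sided 5% test has power of 7%, 12% or 35% to detect a doubling from r = 5%, 10% or 15%.

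**4. What 10 children can support.** Estimation with exact two-sided 95% intervals:
- 0/10: 0 to 30.8%
- 1/10: 0.3% to 44.5%
- 2/10: 2.5% to 55.6%
- 3/10: 6.7% to 65.2%

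**The case against.** The strongest reply is that the protocol largely protects itself. The objective is only to evaluate safety, the analysis is descriptive and between arms, and no test, margin or pass/fail rule is stated. Outcome 5 therefore cannot formally fail, and an unsupported claim would have to come from the report. Outcome 6 on PROMIS-57 is also phrased as a hoped-for result, which suggests a drafting habit and not a hypothesis. Exact intervals could be left to a statistical analysis plan.

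Much of this stands. The descriptive analysis suits the sample, and the intervals are a useful reporting detail whose absence is no error. But the protocol itself fixes both the outcome and the analysis sentence, and they ask different questions. An analysis plan could add detail, but it would not make the outcome as worded attainable with 10 children.

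A reader might go further and infer that the outcome is almost certain to fail. Treating the twelve side effects in section 3.3 as independent, at a common rate of 3%, gives 1 − (1 − 0.263)^12 = 97% for at least one chance excess, and more at the other rates. The protocol does not support that figure:
- The list covers patients from age 3 into adulthood, whereas outcome 5 refers to children.
- Outcome 5 does not say that every event type must separately stay within its reference rate.
- Several listed effects are plainly related (somnolence and fatigue, respiratory infection and fever), so independence is doubtful.

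With four types, the number that section 2.1 names as additional effects at ages 3 to 7, the same arithmetic gives about 70% (1 − 0.737^4) to 96% (1 − 0.434^4). Under complete dependence it returns to the single-type 26% to 57%. No overall failure probability should be quoted.

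**Conclusion.** The point holds as a fault in the wording of a secondary outcome. Outcome 5 names a comparison with the monograph that section 3.10 does not make, and it claims a demonstration that about 10 exposed children cannot deliver for most event types. The firm figure is the zero-event upper limit of 26% (one-sided) or 31% (two-sided). It rests only on n = 10 and binomial sampling, and it falls to 19% to 22% one-sided with 12 to 14 exposed.

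The chance-exceedance figures rest on assumed reference rates and serve as illustration. The impossibility is not universal: for an event with a reference rate above about 26% to 31%, a count at or near zero could support non-excess. Nor does the point show that gabapentin is less safe in these children, or that the descriptive comparison is unsuitable. The primary conclusion is not affected.

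**What to change.** In section 3.4 and in the Trial Summary, restate outcome 5 along these lines: number and proportion of children with each adverse event on gabapentin and on placebo, compared within child and described with exact 95% intervals. Remove the wording that presents non-excess over the monograph as something to be demonstrated. If monograph frequencies are mentioned, give them as context without a conclusion of no excess.

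This brings the outcome into line with the objective in section 2.2 and the analysis in section 3.10. It costs one sentence in two places and changes no data collection, visit or treatment. The price is a more modest safety claim: the trial will describe adverse events with wide intervals and will not certify them against an external rate.
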